### Brain Stimulation and Drug Administration Experimental Sessions (Visits 2-7):

Experimental sessions during Experiments 1 and 2 will last approximately 7 hours and test 6 combinations of TMS and THC on relevant outcome measures (Visits 2-7; Figure 1). Subjects in Experiment 1 will receive real and sham excitatory iTBS of the left DLPFC. Subjects in Experiment 2 will receive real and sham inhibitory cTBS of the left DLPFC. A single bout of iTBS or cTBS (real or sham) TMS will be delivered at a single time point (approximately 3 hours after capsule administration) during each experimental session. Subjects will receive the 6 experimental conditions in random order except that the combination of 30 mg THC + active TMS condition (iTBS or cTBS) will not be administered prior to the administration of 30 mg THC + sham TMS.

Drug Administration: THC (10 and 30 mg) and placebo will be administered orally under double-blind conditions. The oral route was chosen to maintain subject and research staff blindness and to eliminate any expectations that may accompany other routes of drug administration (i.e., smoking). Subjects will ingest capsules with approximately 150 mL of water. Research staff will conduct a mouth check to ensure that the subject swallowed the capsules. Placebo will also be tested and capsules will be filled with a behaviorally inert substance (e.g., corn starch). If heart rate is above 100 bpm before dose administration, the dose will be withheld and heart rate reassessed every 15 minutes for 1 hour. If heart rate has not fallen below 100 bpm after 1 hour, the study physician will be consulted regarding the subject's continued participation in the study.

The doses of THC will be 10 and 30 mg. Capsules will contain commercially available delta-9-THC (Marinol; dronabinol). This active dose was chosen based on our previous laboratory research with THC in humans (Lile et al., 2009, 2010a, 2010b, 2011, 2012a, 2012b, 2013, 2014, 2015). For comparison, the therapeutic dose range indicated for antiemesis is 5-20 mg administered 4-6 times per day. The starting therapeutic dose range indicated for appetite stimulation is 2.5-10 mg administered prior to lunch and dinner, but this can be increased up to 20 mg. We have previously administered up to 90 mg THC acutely (Lile et al., 2013) in individuals with less cannabis experience than proposed in the present study. Plasma concentrations for oral THC peak from 2-4 hours, which is consistent with the proposed experimental procedures (Hollister et al., 1981). The half-life of THC is 19-36 hours, but the duration of the psychoactive effects last only 4-6 hours (Hollister et al., 1981; Lemberger et al., 1972).

**TMS Coil Placement and Stimulation Parameters:** For real and sham sessions in both experiments, rMT will be determined before the delivery of iTBS (Exp. 1) and cTBS (Exp. 2) using standard single-pulse motor mapping procedures (described above) during each experimental session. Determination of rMT before delivery of TMS (i.e., iTBS or cTBS) during each session is necessary because rMT varies across individuals and in response to various environmental and individual factors (e.g., across days and times of day, amount of sleep) and ensures that the minimum necessary stimulation intensity is used during the TMS protocol during each experimental session. rMT will be determined after check-in procedures have been completed, prior to capsule administration.

A two-sided, MagVenture Cool-B65 active/placebo coil will be used to deliver active (real) and sham TMS during experimental sessions. This coil is specifically designed to facilitate double-blind research experiments in that the administrator does not know which side of the coil is active. Instead, the administrator relies on protocol numbers and a gyrometer internal to the coil to determine the appropriate coil orientation for a given session. Standard 10-20 international EEG coordinates and neuronavigation technology will be used to place the TMS coil over the left DLPFC. The international 10-20 EEG coordinate system will be used to locate the F3 region (corresponding with the DLPFC) and each subject's structural MRI scan, collected during the training session, will be uploaded into functional neuronavigation software (Brainsight; Rogue Research Inc., Montreal, Quebec, Canada) that is integrated with real-time, infrared tracking equipment. The neuronavigation system will be used to refine the position of the TMS coil to minimize the distance between the center of the coil and the subject's cortical tissue.

Theta-burst stimulation (TBS) protocols deliver 3-pulse bursts of TMS at a frequency 50 Hz, repeated every 200 milliseconds (i.e., 5 Hz), and differentially modulate neuronal activity depending on whether bursts of pulses are delivered intermittently (i.e., iTBS; excitatory) or continuously (i.e., cTBS; inhibitory). These TBS parameters mimic endogenous theta rhythms that are associated with the induction of long-term potentiation (LTP) and long-term depression (LTD) mechanisms implicated in learning and memory (Huang et al., 2005).

Subjects will receive a single bout of real or sham TBS during each experimental session that will occur approximately three hours after THC administration (see Figure 1). This time point coincides with the approximate time at which THC concentration in plasma reaches its peak. During each session involving real, excitatory iTBS sessions in Experiment 1, the active side of the coil will face inward directly over the stimulation target (left DLPFC) and the iTBS600 stimulation protocol will be delivered. The excitatory iTBS600 protocol consists of twenty, 2-second trains (10 TBS bursts; 30 pulses/train) repeated every 10 seconds (8 second inter-train interval) across a total of 190 seconds (Huang et al., 2005; Wischnewski and Schutter, 2015). This iTBS protocol recently received FDA approval for the treatment of medication resistant major depressive disorder (FDA 510(k): K173620). During each session involving real, inhibitory cTBS in Experiment 2, the active side of the coil will face inward directly over the stimulation target (left DLPFC) and the cTBS600 stimulation protocol will be administered. The cTBS600 protocol consists of one, uninterrupted, 40-second train of 3-pulse bursts presented at 5 Hz, for a total of 600 pulses (Huang et al., 2005). Comparable TBS parameters have been used previously to modulate executive functioning and motor cortex excitability (see Chung et al., 2016 and Lowe et al., 2018 for reviews). The effects of TBS on executive function last approximately 50-60 minutes after stimulation (Huang et al., 2005; Wischnewski and Schutter, 2015). During all TMS sessions, the target amplified iTBS and cTBS pulse outputs will be 120% of rMT. Importantly, this output intensity setting is the same as that in the FDA-approved iTBS protocol used clinically and we have successfully delivered TMS at 120% of rMT in another IRB-approved protocol (IRB: 44178) without untoward effects. However, the final amplifier output intensity setting for each subject may be reduced from 120% of rMT (final pulse output intensity range of 80-120% of rMT) to increase tolerability, minimize subject discomfort, and improve subject satisfaction with study procedures. To further promote subject comfort and satisfaction with study procedures, a ramp-up procedure that gradually increases the amplifier output intensity from 80% of the target stimulation intensity up to the final pulse output intensity (maximum: 120% of rMT) will be used. The ramp-up procedure will consist of an additional 300 pulses following the same pulse sequence parameters described above (adding approximately 20 or 100 seconds to the total stimulation period length for cTBS and iTBS, respectively) that immediately precede the 600 pulses delivered for iTBS600 and cTBS600. Thus, subjects will receive a total of 900 TMS pulses in each real/active TBS session, 600 of which will be delivered at the target pulse output intensity. Although we do not have other IRB-approved protocols that have used a ramp-up procedure, they are commonly used to enhance the tolerability of TMS procedures (e.g., Hanlon et al., 2017; Kearney-Ramos et al., 2018).

During all sham TMS sessions, the placebo side of the coil will be positioned over the left DLPFC as described above, however the active side of the coil faces outward and a magnetic field does not pass through the skull. For both real and sham sessions, small electrodes are placed approximately 4 to 5 cm apart on the forehead on either side of the TMS target location. These electrodes pass small electrical currents subcutaneously (under the skin but not through the skull) in synchronization with the pulse sequence of the TMS procedure. This allows subjects to experience skin sensations akin to the real TMS protocol (e.g., slight tingling and/or itching and

twitching) during the sham session to facilitate experimental blinding.

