**Short Title Description**

Please use a few key words to easily identify your study - this text will be displayed in the Dashboard listing for your study.

TMS in Emerging Adults with CUD

Anticipated Ending Date of Research Project: 6/30/2024

Maximum number of human subjects (or records/specimens to be reviewed) 80

After approval, will the study be open to enrollment of new subjects or new data/specimen collection?  Yes  No

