### Study Design

Describe and explain the study design (e.g., observational, secondary analysis, single/double blind, parallel, crossover, deception, etc.).

- *Clinical Research:* Indicate whether subjects will be randomized and whether subjects will receive any placebo.
- *Community-Based Participatory Research:* If you are conducting [community-based participatory research \(CBPR\)](#), describe strategies for involvement of community members in the design and implementation of the study, and dissemination of results from the study.
- *Qualitative research:* Indicate ranges where flexibility is needed, if a fixed interview transcript is not available, describe interview topics including the most sensitive potential questions.
- *Research Repositories:* If the purpose of this submission is to establish a Research Repository (bank, registry) and the material you plan to collect is already available from a commercial supplier, clinical lab, or established IRB approved research repository, provide scientific justification for establishing an additional repository collecting duplicate material. Describe the repository design and operating procedures. For relevant information to include, see the [UK Research Biospecimen Bank Guidance](#) or the [UK Research Registry Guidance](#).

A double-blind, sham- and placebo-controlled, 2x2x3 mixed-factorial design will be used to assess the impact of excitatory and inhibitory TMS (real and sham) of the DLPFC on decision-making, working memory, subjective drug effects, and physiology following acute administration of oral THC (0, 10, and 30 mg) in two experiments. Each experiment will consist of one training and six experimental sessions. Subjects in Experiment 1 will receive real and sham excitatory intermittent theta-burst stimulation (iTBS) in combination with each dose of oral THC. In Experiment 2, subjects will receive real and sham inhibitory continuous theta-burst stimulation (cTBS) combined with each dose of oral THC. Under this arrangement, TMS Protocol (iTBS or cTBS) is a between-subjects factor whereas TMS Type (real and sham) and THC dose (0, 10, and 30 mg) are within-subjects factors. Figure 1a (attached) shows a diagram of the experimental design.

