#### Data Collection & Research Materials

In this section, please provide the following:

- Describe all sources or methods for obtaining research materials about or from living individuals (such as specimens, records, surveys, interviews, participant observation, etc.), and explain why this information is needed to conduct the study.
- For each source or method described, please list or attach all data to be collected (such as genetic information, interview scripts, survey tools, data collection forms for existing data, etc.).
- If you will conduct a record or chart review, list the beginning and end dates of the records you will view.

Neuroimaging data will be acquired on a Siemens 3-Tesla (3T) PRISMA scanner. A high-resolution (1 cubic millimeter voxels) T1-weighted MP-RAGE structural image will be acquired for each subject. Functional images will be acquired using echo-planar imaging. Hyper-angulated volumes will be acquired with 37 ascending and interleaved slices at an angle 30-degrees to the anterior-posterior commissure to prevent OFC washout. Additional parameters will be similar to those used in other approved neuroimaging protocols in our lab (e.g., a repetition time (TR) of 2 seconds, echo time (TE) of 25 ms, a flip angle of 90 degrees, and functional voxels of size 3.4mm x 3.4mm x 4.0mm). Image preprocessing will be performed in statistical parametric mapping (SPM) 12 software using standard procedures (see Wesley et al., 2014). Data from functional scans will be treated similarly to fMRI data in previous studies (e.g., slice-timing corrected, head-motion corrected, warped into MNI standard space, re-sliced to 4 cubic millimeter voxels and smoothed with an 8mm full-width, half-maximum (FWHM) Gaussian kernel).

**Experimental Session Outcomes:** Physiological outcomes will include measurements of heart rate and blood pressure collected at hourly intervals throughout the session before each block of experimental tasks. Performance will be measured on 4 experimental tasks at baseline (approximately 30 minutes after arrival; 1 hour before THC administration) and immediately following TMS (approximately 4.5 hours after arrival; 3 hours after THC administration) (Figure 1).

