Task 3: The N-Back (N-Back) task is a validated working memory task (Jaeggi et al., 2010). Subjects are presented with a sequence of letters and must indicate when the letter currently being viewed matches the one from N steps earlier in the sequence. The load factor "N" is adjusted to make the task more or less difficult. Adjusted accuracy and reaction times on rounds of, 0-, 1-, 2-, and 3-Back are the primary outcomes.

Task 4: The Cannabis Purchasing Task (CPT) is an adaptation of an established hypothetical alcohol purchasing task (Amlung et al., 2015). Subjects are asked how many puffs of their preferred cannabis they would consume at 21 prices, ranging from free to \$20/unit. Primary outcomes of this task include elasticity of demand (a or "alpha") and intensity of demand ( $Q(0)$  or "Q naught"). These values are derived using nonlinear regression with the exponential demand equation (Hersh & Silberberg, 2008):  $\log(10)Q = \log(10)(Q(0)) + k(e^{-a*Q(0)*C}) - 1$ , where  $Q$  = consumption at a price;  $Q(0)$  = derived intensity of demand (consumption at zero price);  $k$  = a constant that denotes the range of consumption values in  $\log(10)$  units;  $C$  = the price of the commodity; and  $a$  = derived essential value (a measure of elasticity of demand). Greater values of  $Q(0)$  indicate greater consumption at unconstrained price (i.e., a theoretical price of zero). Greater values of  $a$  indicate a higher elasticity of demand or change in consumption with change in unit price.

**Behavioral Data Analyses:** Analysis of variance (ANOVA) will be used to compare group demographic data, data from primary outcome measures (above), and the primary molar PRLC task outcome, amount of money earned on the task. Data from the cannabis purchasing task (CPT) will be analyzed using the exponential demand equation (Hersh & Silberberg, 2008) described above. Molecular PRLC results will be analyzed using RL modeling of trial-by-trial data (Sutton & Barto, 1998), which uses the history of reinforcement for each choice, expressed as an expected value, to predict future choices. The value of the chosen option (option A) is updated via the outcome of the trial according to Equation 1 (see Figures attachment), where the updated value of option A is

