### Data and Safety Monitoring

The IRB requires review and approval of data and safety monitoring plans for greater than minimal risk research or NIH-funded/FDA-regulated clinical investigations.

- If you are conducting greater than minimal risk research, or your clinical investigation is NIH-funded, describe your Data and Safety Monitoring Plan (DSMP). [Click here for additional guidance on developing a Data and Safety Monitoring Plan](#).
- If this is a non-sponsored investigator-initiated protocol considered greater than minimal risk research, and if you are planning on using a Data and Safety Monitoring Board (DSMB) as part of your DSMP, [click here for additional guidance](#) for information to include with your IRB application.

The purpose of this project is to understand the neural mechanisms of cannabinoid-impaired decision-making and associated neurocognitive processes. Randomized, double-blind, placebo-controlled (for drug), sham-controlled (for brain stimulation), within-subjects designs will be employed. Subjects will be forty (N = 40) men and women of various race/ethnicity, aged 18-34, who report daily or near-daily cannabis use (i.e., at least 20 days in the last month) and meet criteria for cannabis use disorder but are not seeking treatment for their drug use. All subjects must provide informed consent to participate. This sample will be recruited from the local community and will participate as outpatients at the NSL and MRISC.

The proposed experiments will examine the ability of non-invasive brain stimulation (TMS) to impact the acute effects of THC on specific neurocognitive outcomes. These experiments will also use neuroimaging to model the regional and interconnected functional brain profiles that predict individual differences in the specific and combined effects of THC and/or brain stimulation on experimental outcomes. Together, the proposed studies will advance the understanding of neural mechanisms contributing to maladaptive decision-making that promotes habitual cannabis use and the development of cannabis use disorder in young adults.

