#### Data Monitoring Plan:

Data from experimental sessions will be collected using a computerized data collection and management system. This system automates the collection of the behavioral and physiological data, which ensures the accuracy and completeness of data collection. The data are stored in a unique file on the hard-drive of the computer and are electronically backed-up at the end of each session. In all instances, the data files do not contain the name of the subject; but instead, each subject is identified by a unique four-digit number. The computer file linking subject names and numbers will be encrypted and only key personnel will have access. Data files for experimental tasks and physiological measures from each experimental session will be managed and combined into a single electronic spreadsheet by automated macros. Data will then be combined into a single electronic spreadsheet and separated by experimental measure for statistical analysis using SPSS (Statistical Package for the Social Sciences, IBM Corp.) software. Neuroimaging data will be stored and backed-up on encrypted and secure servers at the MRISC according to existing and approved UK protocols. Secure copies of structural and functional neuroimaging data sets will be securely routed to the PI's office computer via encrypted network protocols occurring behind the UK firewall. These data will be analyzed using customized Matlab (MATLAB) scripts and an array of neuroimaging software packages, including but not limited to SPM and FSL primary platforms and their associated neuroimaging toolboxes.

The primary outcomes for both experiments are those from neurocognitive tasks measuring decision-making and working memory. Subjective drug effects will also be measured. Changes in outcome variables following active drug and placebo administration will be compared between real and sham transcranial magnetic stimulation (TMS) to determine if excitatory iTBS600 (Exp.1) or inhibitory cTBS600 (Exp. 2) delivered to the left dorsal lateral prefrontal cortex (DLPFC) alters the effects of THC on study outcomes. Data will

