be analyzed using ANOVA with alpha set at 5%. Additionally, functional neuroimaging data from Training Sessions in each experiment will be modeled using traditional mass-univariate approaches (e.g., general linear models and statistical parametric mapping) and newer multivariate pattern analysis (i.e., support vector machine learning) to classify the brain profiles that predict the ability of THC and brain stimulation to impact neurocognitive outcomes.

The quality of manipulated data and data analyses will be monitored by random inspection by the PI and/or other key personnel. Preprocessing and analysis of subject-specific behavior and brain data will begin as individual data are collected. Interim analysis of group data will begin once 25% of the sample is accrued.

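### Sham always precedes real TMS at 30 mg THC, but the planned ANOVA names no visit term and does not define the outcome as change from the same-day baseline

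*Combined protocol and SAP*

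**What the plan says.** Under Research Procedures (Brain Stimulation and Drug Administration Experimental Sessions), each subject receives six conditions, one per visit, in random order with one restriction: "30 mg THC + active TMS condition (iTBS or cTBS) will not be administered prior to the administration of 30 mg THC + sham TMS".

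Study Design describes a 2x2x3 mixed design in which TMS Protocol (iTBS or cTBS) is between subjects and "TMS Type (real and sham) and THC dose (0, 10, and 30 mg) are within-subjects factors". No other factor is named.

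Data Collection & Research Materials provides a baseline in every session: "Performance will be measured on 4 experimental tasks at baseline (approximately 30 minutes after arrival; 1 hour before THC administration) and immediately following TMS". For the analysis it says: "Analysis of variance (ANOVA) will be used to compare group demographic data, data from primary outcome measures (above"). Learning-model parameters go to linear mixed modelling with no terms listed.

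The Data Monitoring Plan says: "Changes in outcome variables following active drug and placebo administration will be compared between real and sham transcranial magnetic stimulation (TMS"), and that data will "be analyzed using ANOVA with alpha set at 5" percent. It does not say what the change is measured from. No section names a visit, session, period or sequence term.

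On size, Data and Safety Monitoring says "Subjects will be forty (N = 40) men and women", while the project information page gives "Maximum number of human subjects (or records/specimens to be reviewed) 80". No number per experiment, power calculation, SD or expected visit effect is given.

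**The concern.** The Objectives ask whether TMS can block the effects of THC. The real-sham comparison at the highest dose bears on this most directly, and it is the only dose at which order is not balanced by randomisation. With no visit term, anything that shifts across the six sessions enters that contrast and the TMS x dose contrast.

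Two kinds of shift matter:

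- **Practice on the tasks.** If post-TMS scores are analysed, residual improvement favours the later, real-TMS session. Exposure at the training visit should reduce this but may not remove it. A practice shift common to both assessments in a session cancels if change is analysed.
- **A changing response to THC.** If the response wanes over sessions, real TMS appears to block it. Change scores do not remove this.

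Separately, sham versus real TMS at 30 mg coincides exactly with first versus second 30 mg exposure.

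**Working it through.** The plan has no figure of its own on this point, so there is none to reproduce.

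**1. Position imbalance (exact).** Six conditions have 720 orders, of which 360 obey the rule. Treating these as equally likely (an assumption), mean session position is 2.33 for 30 mg + sham, 4.67 for 30 mg + real and 3.50 for each of the other four. The gap between the two 30 mg sessions is 1, 2, 3, 4 or 5 in 120, 96, 72, 48 and 24 orders:

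- mean gap = (120 + 192 + 216 + 192 + 120)/360 = 840/360 = 2.33
- variance = (120 + 384 + 648 + 768 + 600)/360 − 2.33² = 7 − 5.44 = 1.56

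**2. Bias from a linear drift b per visit, no visit term.**

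- 30 mg real-sham: 2.33b
- TMS x dose (30 versus 0 mg): 2.33b − 0 = 2.33b
- TMS main effect: 2.33b/3 = 0.78b
- If the shift is confined to the first visit, the 30 mg bias is one third of it, because 30 mg + sham is first in one third of orders and 30 mg + real never is.

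**3. Type I error.** Assumptions: no true TMS effect, independent residuals with SD 1, two-sided 5% paired tests within an experiment, equal split between experiments. The noncentrality is √n·b·m/√(v + b²w), where m and w are the mean and variance of the position contrast and v is its residual variance:

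- 30 mg: m = 2.33, v = 2, w = 1.56
- interaction: m = 2.33, v = 4, w = 8.56
- main effect: m = 0.78, v = 2/3, w = 1.73

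Example, 30 mg, n = 20, b = 0.10: 4.472 × 0.2333/√2.0156 = 0.735 on 19 df, giving 10.7%.

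| n per experiment | b (residual SD per visit) | 30 mg contrast | TMS x dose | TMS main effect |
|---|---|---|---|---|
| 20 | 0.05 | 6% | 6% | 6% |
| 20 | 0.10 | 11% | 8% | 7% |
| 20 | 0.20 | 28% | 16% | 12% |
| 40 | 0.05 | 8% | 7% | 6% |
| 40 | 0.10 | 17% | 11% | 9% |
| 40 | 0.20 | 52% | 28% | 20% |

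The n = 40 rows use the maximum of 80 subjects. Simulation of the 30 mg contrast (3,000 runs per setting, n = 20) gave 11.3% at b = 0.10 and 29.3% at b = 0.20. Without the order rule, b = 0.20 gave 4.5%.

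For scale, 0.10 total SD per visit is 0.10/√(1 − ρ) residual SD: 0.14 at within-subject correlation 0.5 and 0.18 at 0.7.

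**4. What a categorical visit term removes.** Bias in the 30 mg contrast, all permitted orders equally represented, b = 0.10 or a second-exposure shift of 0.30:

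| Source | No visit term | Visit term | Visit + linear visit x dose |
|---|---|---|---|
| Additive drift, all sessions | 0.23 | 0 | 0 |
| Drift in THC sessions only | 0.23 | 0.09 | 0 |
| Drift at 30 mg only | 0.23 | 0.18 | 0 |
| Second 30 mg exposure | 0.30 | 0.30 | 0.30 |

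Under additive drift, type I error with the visit term was 4.5-5.7% in simulation for b from 0 to 0.3.

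**5. Precision.** Relative to no visit term, the SE of the 30 mg contrast is 1.09 over all 360 orders and about 1.12 at n = 20. With visit x dose it is 1.48 and about 1.55. The 10 mg contrast is unchanged when all orders are equally represented.

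**The case against.** The best counter-argument is that the plan probably intends change scores. It calls the pre-capsule assessment a baseline and speaks of changes in outcomes. On that reading, additive practice already cancels. What remains is drift in the THC response and the second-exposure effect, which are what a visit term handles least well. The model that does remove linear response drift costs about half as much SE again.

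Much of this stands. The fair criticism on baseline is that the reference point is undefined, not that the baseline is ignored. The visit term is a partial remedy, and a 9-12% larger SE means roughly 18-25% more variance. But the intended reading has to be written down, and even if it is, response drift is left unaddressed.

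Three further points:

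- **Drift size is assumed.** At b = 0.05 the inflation is small. The 28% figure needs a cumulative shift of 5 × 0.20 = 1 residual SD from the first session to the sixth. The imbalance itself is certain: at least one visit under any scheme that obeys the rule.
- **No 30 mg paired test is named.** In the full mixed ANOVA with 40 subjects, tests involving TMS Protocol stay near 5%, because drift common to both experiments cancels. The pooled TMS x dose test does not: it reaches about 7%, 11% and 28% at the three values of b. The Data Monitoring Plan also asks about real versus sham within each experiment.
- **Equal residual variance is assumed.** A single subject random effect could misstate the SE if variability is greater at 30 mg. This should be checked when the model is fitted.

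**Conclusion.** The concern holds. The order restriction, the absence of any visit term and the undefined reference point for change all follow from the text. The 2.33-session mean gap is exact if the permitted orders are equally likely. The consequence depends on an unstated drift: at 20 per experiment, type I error for the 30 mg contrast is about 6% to 28% for drifts of 0.05 to 0.20 residual SD per visit. Those rates apply if post-TMS scores are analysed, or if change is analysed and the THC response itself drifts in the same additive way. The Figure 1 and Table 1 attachments were not available to check. This should be fixed: the exposed contrast is central to the objective, and the remedy needs no new data. No analysis can separate second 30 mg exposure from real TMS within an experiment.

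**What to change.** The ordering rule is a matter for the clinical team. The following changes are to the analysis plan only and should be settled before the group interim analysis at 25% accrual.

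1. Define each task outcome as change from the same-day pre-capsule score, or name covariate adjustment instead, and fix that choice in advance. Analyse it in a linear mixed model with TMS Protocol x TMS Type x THC dose, a subject random effect and experimental session number (1-6) as a categorical fixed effect. Apply the same terms to the learning-model parameters.
2. Add a linear visit x THC dose term as a sensitivity analysis for drift in the THC response.
3. State that first versus second 30 mg exposure is fully aliased with sham versus real TMS and that no visit term removes this. Do not report the within-experiment 30 mg contrast as a randomised-order comparison. Read it beside the 10 mg contrast, whose order is unconstrained.
4. Report the iTBS-minus-cTBS difference at 30 mg only as supportive. It assumes the same exposure-order effect in both experiments and answers a different question.

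Cost: no change to visits or data. The SE of the 30 mg contrast rises about 9-12% in the main model. It rises 48-55% in the sensitivity model, which is why that model should not be primary. The iTBS-minus-cTBS contrast has an SE about 41% larger (√2 with equal groups).
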